2. STUDY DESIGN

2.1. Synopsis of Study Design

This is a randomized, double-blind, placebo-controlled, Phase 3, multisite study of edasalonexent in pediatric patients with DMD.

[figure not shown]
Eligible patients will be ambulatory boys aged ≥ 4.0 to < 8.0 years with a confirmed diagnosis of DMD who have not use steroids within 24 weeks prior to treatment start (Day 1). In regions where eteplirsen is approved or there is an established access program, patients who have received at least 24 weeks of treatment with eteplirsen prior to Day 1 will be eligible.

As shown in [Figure 1](#), following a 4-week screening period to determine eligibility, approximately 126 patients will be randomized 2:1 to receive edasalonexent 100 mg/kg/day or placebo in a double-blind fashion daily for 52 weeks. Randomization will be stratified by baseline age (≤ 6.0 vs. > 6.0 years), baseline time to stand from supine (≤ 5 vs. > 5 seconds), treatment with eteplirsen (yes vs. no), and region (North America vs. Europe/Asia/Australia). Note that if siblings are enrolled, they will be assigned to the same treatment group.

Randomized patients (and enrolled siblings who are not randomized) will complete Baseline procedures and begin receiving study drug (edasalonexent or placebo) on Day 1. During the treatment period, patients will have site visits approximately every 13 weeks with site calls in between as specified in the Schedule of Assessments ([Table 1](#)). For those patients who do not enter the extension study, a safety follow-up should occur within 2 weeks of the last dose of study drug for collection of adverse events (AEs).

The length of a patient's participation in the study will be from the time of informed consent through the Week 52 visit. A patient will be considered to have completed the study when they have completed the Week 52 assessments. Patients who do not participate in the open-label extension study will be considered to have completed the study after they complete the safety follow-up.

Figure 1 Overview of Study Design

2.2. Randomization Methodology

Patients will be randomized 2:1 to receive edasalonexent or placebo in a double-blind fashion. Randomization will be stratified by Baseline age (≤ 6.0 vs. > 6.0 years), baseline time to stand

from supine (≤ 5 vs. > 5 seconds), treatment with eteplirsen (yes vs. no), and region (North America vs. Europe/Asia/Australia). Note that if siblings are enrolled, they will be assigned to the same treatment group.

Any mis-categorization of a patient's randomization strata (i.e., a patient being assigned to an incorrect randomization strata relative to their actual study data) will be presented in a listing. Analyses by strata (i.e., see [Section 4.10.8](#)) will be based on the randomization strata values.

2.3. Unblinding

After completion of the study, patients, monitors, Investigators, study center personnel, and the Sponsor will remain blinded to treatment assignments until results from the study are available.

2.4. Study Procedures

The schedule of assessments, as outlined in the study protocol, is provided in [Table 1](#).

Table 1: Schedule of Assessments

	Screen ^a	BL ^b	Double Blind, Placebo-Controlled Treatment (Weeks 1 - 52)									Safety F/U ^c
Study Week(s)	-4 - 0	0	3	6	13	19	26	32	39	45	52/ET ^d	
Informed Consent/Assent	X											
Site Visit ^e	X	X			X		X		X		X	
Site Call ^{e,f}			X	X		X		X		X		X
Med History/Demographics	X											
Confirm Eligibility	X	X										
Randomization ^g		X										
Vital Signs	X	X			X		X		X		X	
Weight	X	X			X		X		X		X	
Height		X					X				X	
Physical Examination	X	X			X		X		X		X	
AEs/Con Meds/Change in Function ^h	X	Continuous										
12-Lead ECG ⁱ	X						X				X	
Cardiac Monitoring ^j		X					X				X	
Hematology/Chemistry ^k	X	X			X		X		X		X	
ACTH/Cortisol ^k		X			X		X		X		X	
Urinalysis	X						X				X	
DNA Sample ^l		X										
Biomarkers, Gene Expression ^k		X			X		X		X		X	
NSAA, Stand from Supine, 10MWT, 4-Stair Climb, Muscle Strength, PUL ^l	X	X			X		X		X		X	
Videotape Functional Assessments ^m	X	X									X	
PODCI ⁿ		X									X	
Lateral Spinal Radiography, DXA ^o		X									X	
Nutritional Guidance ^p		X										
Drug Dispensation		X			X		X		X			
Drug Accountability			X		X		X		X		X	
Plasma PK ^q		X			X		X				X	

a Per Investigator's discretion, informed consent, medical history/demographic data and lab assessments may be completed remotely by a qualified medical professional.

- b The first day of study drug is “Day 1”; unless otherwise specified, all assessments should be completed within a 4 week window prior to Day 1.
- c Safety follow-up should occur within 2 weeks after the last dose of study drug. Patients continuing into the open-label extension study are not required to perform the safety follow-up.
- d If patient discontinues treatment early, patient will be asked to return for early termination (ET) visit prior to their last dose of study drug. Functional assessments performed within 6 weeks of discontinuing treatment do not need to be repeated at the ET visit. If the ET visit occurs after drug has been discontinued, certain assessments may be omitted per Sponsor discretion.
- e Weeks 6-19 should be conducted within the study week with a ± 4 -day window. Weeks 26-54 have a ± 10 -day window.
- f Per Investigator discretion, site calls may occur by telephone or use of other technology.
- g Randomization occurs after Screening assessments have been completed and eligibility is confirmed.
- h AEs and concomitant medication/therapy will be assessed at all visits and during site calls.
- i ECGs will be performed predose at all timepoints. At Week 26, ECG will be performed predose and 2 hours postdose (± 15 min).
- j Cardiac monitoring will be performed for approximately 48 hours remotely via a wearable cardiac monitoring device if approved for use in the participating country.
- k Blood samples will be drawn in the morning when possible.
- l A DNA sample may be collected at Baseline for drug metabolizing enzyme and/or transporter analysis as well as pharmacogenomic analysis of potential markers of clinical risk/benefit.
- m These assessments should be performed in the order listed and in the morning when possible. Time to stand from supine and 10MWT will be recorded as measured in the NSAA.
- n The PUL 6-point entry item scale will be performed at all timepoints. If a patient scores a 6 on the PUL entry item scale, no further PUL testing is required for the visit.
- o Videotaping at Baseline is required if Screening video did not pass QC.
- p PODCI will be performed when feasible.
- q These assessments should be collected within 2 months prior to Day 1. In Germany, bone assessment will not be performed until the respective approvals from the German Federal Office for Radiation Protection (Bundesamt für Strahlenschutz) become available.
- r Patient compliance with the nutritional guidance will be confirmed throughout the trial.
- s Urine PK collection will be performed at Week 13. Plasma PK collection will be performed predose at Week 13 and Week 52. At Week 26 plasma PK collection will be performed predose, 1 hour, 2 hours (± 15 min), and 4 hours postdose.

2.5. Efficacy Estimands

The estimands corresponding to the primary and secondary efficacy objectives are provided in [Sections 2.5.1](#) and [2.5.2](#), respectively.

2.5.1. Primary Objective Estimand

The estimand corresponding to the primary objective for this study is shown in [Table 2](#).

Table 2: Estimand for the Primary Objective

Objective	Efficacy of edasalonexent - NSAA Total Score
Estimand	The expected effect in patients if all patients had adhered to the treatment regimen and did not take any corticosteroid therapy or discontinue treatment.
Population	Full Analysis Population (FAP)
Variable	Change from baseline at Week 52 on NSAA Total Score
Intercurrent Events	Treatment discontinuation or initiating corticosteroid therapy or any approved Duchenne therapy : The study is interested in the treatment effect assuming that patients remained on their treatment regimen throughout the study, without initiating corticosteroid therapy or any approved Duchenne therapy.
Population-level Summary	The population summary for the primary estimand is the mean difference in the Week 52 change from baseline on the North Star Ambulatory Assessment Total Score between the edasalonexent and the placebo treatment groups using the model described in Section 4.10.1 . This summary is computed using the FAP as defined in Section 3.1

2.5.2. Secondary Objective Estimands

The estimands corresponding to the secondary objectives are shown in [Table 3](#).

Table 3: Estimands for the Secondary Objectives

Objective	Efficacy of edasalonexent - 10MWT
Population	FAP
Variable	Change from baseline at Week 52 on the 10MWT speed.
Intercurrent Events	Treatment discontinuation or initiating corticosteroid therapy or any approved Duchenne therapy : The study is interested in the treatment effect assuming that patients remained on their treatment regimen throughout the study, without initiating corticosteroid therapy or any approved Duchenne therapy.

Population-level Summary	The population summary for the estimand is the mean difference in the Week 52 change from baseline on the 10MWT speed between the edasalonexent and the placebo treatment groups. This summary is computed using the FAP as defined in Section 3.1 .
Objective	Efficacy of edasalonexent - Stand from Supine Speed
Population	FAP
Variable	Change from baseline at Week 52 on the stand from supine speed.
Intercurrent Events	Treatment discontinuation or initiating corticosteroid therapy or any approved Duchenne therapy : The study is interested in the treatment effect assuming that patients remained on their treatment regimen throughout the study, without initiating corticosteroid therapy or any approved Duchenne therapy.
Population-level Summary	The population summary for the estimand is the mean difference in the Week 52 change from baseline on the stand from supine speed between the edasalonexent and the placebo treatment groups. This summary is computed using the FAP as defined in Section 3.1 .
Objective	Efficacy of edasalonexent - 4-Stair Climb
Population	FAP
Variable	Change from baseline at Week 52 on the 4-Stair climb speed.
Intercurrent Events	Treatment Discontinuation or initiating corticosteroid therapy or any approved Duchenne therapy : The study is interested in the treatment effect assuming that patients remained on their treatment regimen throughout the study, without initiating corticosteroid therapy or any approved Duchenne therapy.
Population-level Summary	The population summary for the estimand is the mean difference in the Week 52 change from baseline on the 4-Stair Climb speed between the edasalonexent and the placebo treatment groups. This summary is computed using the FAP as defined in Section 3.1 .

2.6. Efficacy Endpoints

2.6.1. Primary Efficacy Endpoint

The primary efficacy endpoint is the CFB in the NSAA Total Score at Week 52.

The NSAA is a clinician-reported outcome instrument designed to measure ambulatory function in males with DMD. During this assessment, patients are asked to perform 17 different functional activities, including a 10MWT, rising from sit to stand, standing on one leg, climbing and descending a step, stand from supine, lifting the head, standing on heels, and jumping. To optimize standardization and consistency of testing, study procedures must be performed by trained evaluators only, with every effort made to have the same clinical evaluator perform all assessments for a given patient, in the same order, at the same time of day, preferably in the morning. Completion of this test is expected to take approximately 20-30 minutes.

Each function activity will be scored as 0 (unable to achieve independently), 1 (modified method but achieves goal independent of physical assistance from another), or 2 (no obvious modification of activity) or “Not Scored”. If the NSAA test was performed and any of the individual items are scored as “not scored” (i.e., for reasons unrelated to the patients physical capabilities), the corresponding total score will be set to missing. The sum of these 17 scores will be used to form an ordinal total score (range 0 – 34).

2.6.2. Secondary Efficacy Endpoints

The 3 secondary efficacy endpoints are:

- The CFB in the 10MWT speed at Week 52
- The CFB in the stand from supine speed at Week 52
- The CFB in the 4-stair climb speed at Week 52

The 10MWT measures time to walk a distance of 10 meters. The stand from supine and 4-stair climb tests measure the amount of time taken to complete those tasks. To optimize standardization and consistency of testing, study procedures must be performed by trained evaluators only, with every effort made to have the same clinical evaluator perform all assessments for a given patient, in the same order, at the same time of day, preferably in the morning. Completion of timed function tests (TFTs) is expected to take approximately 10 minutes.

For all TFTs, both the times to complete (seconds) and the speed of completing the tests (i.e., calculated as the reciprocals of the time to complete; $\text{speed} = 1/\text{time}$) will be provided. If there are any patients not able to complete the test (reason not done = “subject physically unable to complete test”), a value of 0 will be assigned for the reciprocal test (i.e., speed; in units of task per second). For the “time to complete” endpoints, a value of 12 seconds will be imputed.

Additionally, for the 3 TFTs, the time will be set to 12 seconds and the speed to 0 if the TFT assessment meets the following TFT grading criteria (i.e., each of the TFTs is “graded”):

- 10MWT: a Grade of 1 or 2 (from a 6-point scale)
 - 1=Unable to walk independently
 - 2=Unable to walk independently but can walk with knee-ankle foot orthoses or support from a person
- Stand from Supine: a Grade of 1 or 2 (from a 6-point scale)
 - 1 = Unable to stand from supine, even with use of a chair
 - 2 = Assisted Gowers – requires furniture for assist in arising from supine to full upright posture (no time to be recorded)
- 4-Stair Climb: a Grade of 1 (from a 6-point scale)
 - 1 = Unable to climb 4 standard stairs (no time recorded)

2.6.3. Additional Efficacy Endpoints

Additional efficacy endpoints include CFB on the following:

- Muscle strength testing
- PUL entry item assessment

- PODCI Transfer and Basic Mobility Scale
- CFB multivariate rank sum score

2.6.3.1. Muscle Strength Testing

Muscle strength testing will include assessment of knee extension and elbow flexion (in kilograms), and will be performed using a hand-held dynamometer. Knee myometry will be performed while the patient is in a sitting position. Elbow myometry will be performed while the patient is positioned supine.

Muscle testing will be performed by trained evaluators; every effort will be made to have the same evaluator perform all assessments for a given patient at the same time of day. Completion of each muscle test is expected to take approximately 10-15 minutes, for a total of 20-30 minutes.

Multiple assessments are taken on the right and left knee and right and left elbow. The following is the algorithm for determining the patients elbow (knee) scores:

- For both the left and right elbow (separately) the peak score (i.e., maximum value) will be used as the value for the patient.
- The average of the maximum right elbow score and maximum left elbow score will be the elbow score for that visit.
- The same algorithm is used for the knee

As such, at each scheduled timepoint, there will be an elbow flexion and knee flexion endpoint for the muscle testing (units of kilogram (kg)).

2.6.3.2. Performance of Upper Limb (PUL) Entry Item Assessment

The PUL (PUL 2.0; [Pane \(2018\)](#)) was specifically designed to assess upper limb function in ambulant and non-ambulant DMD patients. The PUL is made up of a 6-point entry item assessment to define starting functional level, and 22 items subdivided into shoulder level (6 items), middle level (9 items), and distal level (7 items) dimension. Loss of full overhead reach occurs at median age 9.6 years with some boys losing the ability as early as age 5 or 6.

Patients will perform the PUL entry item assessment; based on the age of patients in this study, most patients are expected to score a 6 on the scale of 0 – 6 and will not be required to perform the additional items.

Patients who score below a 6 on the entry item assessment will perform a subset of the PUL battery including the shoulder level dimension and supination, consisting of 7 items with a maximum score of 14. Completion of the 6-point entry item assessment is expected to take approximately 5 minutes. Completion of the battery of PUL assessments is expected to take approximately 20 minutes. Any missing items on the entry item assessment or the subset of the PUL battery will be considered a zero for the purposes of deriving the overall score.

The following endpoints will be analyzed from the PUL assessments

- Item 1 and Item 2 (Summed): this is the sum of Items 1 and 2:
 - Item 1: Shoulder abduction both arms above head “Raise your arms out to the side and above your head– try and keep straight elbows” a 0 – 2 point scale

- Item 2: Raise both arms to shoulder height (elbows at shoulder height) “Raise your arms to shoulder level” a 0 – 2 point scale
- PUL Total Score: The PUL total score is a sum of items 1 -7. Each of the 7 items has a score range from 0 – 2 with a higher score indicating better function. The PUL total score ranges from 0 – 14 with a higher score indicating better functioning.

For patients who score a “6” on Item A (and are not required to perform PUL items 1 – 7), the following data imputation will be performed:

- Items 1 and 2 be imputed with a value of 2
- Items 3, 4, 5, 6, 7 will not be imputed, items will remain missing.
- The PUL Total Score will be not be imputed, the score will be missing.

Due to this missing data issue, the analysis of the PUL Total Score will be performed on the subset of FAP patients who did not score a “6” on Item A. The analysis of Items 1 and 2 (i.e., where scores are imputed for patients who score a “6” on Item A) will be performed on the FAP.

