4.10.3. Additional Efficacy Analyses

Additional efficacy endpoints include CFB on the following:

- Muscle strength testing: 2 endpoints: elbow flexion (i.e., average of the left and right elbows), knee extension (average of the left and right knees). If either the left or right value is missing the value will be the non-missing score.

Note: values which are indicated as not being valid as determined by a response of “No” to “Was test valid? (i.e. representative of child’s true function)” for these assessments will not be included in the analysis (but will be presented in listings).

These additional efficacy endpoints will be analyzed using an MMRM ANCOVA, in a manner similar to that described in [Section 4.10.1](#) with the corresponding baseline muscle strength endpoint replacing baseline NSAA as a covariate.

- **PUL endpoints:** This includes the PUL Total Score, and the sum of individual items 1 and 2 (note these 2 items are imputed for patients who scored a “6” on Item A as defined in [Section 2.6.3.2](#)).

The sum of individual items 1 and 2, and PUL total score endpoints will be analyzed using an MMRM ANCOVA, in a manner similar to that described in [Section 4.10.1](#) with the corresponding baseline PUL score replacing baseline NSAA as a covariate.

PODCI Transfer and Basic Mobility Scale: This additional efficacy endpoint will be analyzed using an ANCOVA. The ANCOVA model will include CFB in the PODCI Transfer and Basic Mobility Scale at Week 52 as the dependent variable, treatment and region (North America vs. Europe/Asia/Australia) as factors, and baseline age (as a continuous variable), baseline time to stand from supine (as a continuous variable), and baseline PODCI Transfer and Basic Mobility Scale score (as a continuous variable) as covariates.

As an additional analysis of the PODCI Transfer and Basic Mobility Scale endpoint, the analysis above will be repeated subset to the subgroup of patients with the same caregiver completing the form at both baseline and Week 52 (i.e., from the PODCI eCRF page “Who completed this form?” with responses of: Caregiver, Father, Mother).

Note that summary statistics will be provided for the additional PODCI scales at each scheduled timepoint.

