This will be determined by the “Remote Efficacy” variable in the Date of Visit eCRF page; a value of “Yes” indicates a response of “Remote”, a value of “No” indicates “Site”. Note there is no remote efficacy at Week 26 (i.e., for Week 26 Remote Efficacy = “No” should be populated in the listing).

- NSAA Performed, 10 MWT Performed, 4SC Performed, TTS Performed, Muscle Strength Performed:

- Yes, No

These variables will be determined by the “was the test performed variables” listed below:

Assessment	SAS Variable
NSAA Performed	MK_NSAA.MKPERF
10 MWT Performed	MK_TFT.WT_MKPERF
4SC Performed	MK_TFT.SCT_MKPERF
TTS Performed	MK_TFT.RFS_MKPERF
Muscle Strength Performed	MK_MST.MKPERF
PODCI Performed	QS_PODCI.QSPERF

- PE Collected, ECG Collected, PK Collected, Biomarkers Collected, Cardiac Monitoring Performed, DXA Performed, Spine Films Performed:
 - Yes, No

These variables will be determined by the “was the test performed variables” listed below:

Assessment	SAS Variable
PE Collected	PE.PEPPERF
ECG Collected	EG.EGPPERF
PK Collected	PC_BL.PCPPERF
Biomarkers Collected	PC_PD.PCPPERF
Cardiac Monitoring Performed	FA_CM.FAPERF
DXA Performed	PR_DXA.PROCCUR
Spine Films Performed	PR_LSR.PROCCUR

There is also a comment field.

Only assessments impacted by COVID-19 will be included.

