5.3. COVID-19 Analyses

The primary and secondary efficacy analysis ([Sections 4.10.1](#) and [4.10.2](#)) will be repeated for the following two sensitivity analyses (i.e., a total of 8 new analyses: 2 sensitivity analyses across the primary and 3 secondary endpoints).

- 1) Excluding all remote efficacy assessments
- 2) Excluding all assessments which occurred during the time period the patient’s site was closed.

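### The SAP scores a missing PUL battery item as 0 whatever the reason, so an item not done for a non-physical reason counts as lost function

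*SAP*

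**What the plan says.** **PUL.** SAP section 2.6.3.2 states: "Any missing items on the entry item assessment or the subset of the PUL battery will be considered a zero". The rule is limited by its purpose only: such an item "will be considered a zero for the purposes of deriving the overall score". No reason for the gap is required. The section then defines the PUL Total Score as the sum of seven items, each scored 0 to 2, with a range of 0 to 14. The exception is a boy who scores 6 on Item A and so skips the battery. His Items 1 and 2 are set to 2, while "Items 3, 4, 5, 6, 7 will not be imputed, items will remain missing", and his Total is missing. The Total is analysed only in boys who did not score 6.

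**NSAA.** SAP section 2.6.1 deals with an item left unscored "for reasons unrelated to the patients physical capabilities), the corresponding total score will be set to missing".

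**Timed tests.** SAP section 2.6.2 gives a speed of 0 when the recorded reason is "subject physically unable to complete test", or when the test has one of the listed grades for being unable or needing assistance.

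**Remote visits.** Protocol Appendix 2 lists PUL among the assessments to be done remotely at Weeks 39 and 52 when the on-site visit is cancelled. It also warns that remote conditions may limit functional testing.

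**COVID-19 analyses.** SAP section 5.3 plans "2 sensitivity analyses across the primary and 3 secondary endpoints". The listing in SAP section 5.2 has fields for "NSAA Performed, 10 MWT Performed, 4SC Performed, TTS Performed, Muscle Strength Performed" and for PODCI, but none for PUL. It does flag remote efficacy visits.

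**The concern.** A score of 0 on a PUL item is the worst possible result for that task. It is the right value when the boy tried and could not do it. It is a false value when the task was not attempted because of space, camera position, time or cooperation. The rule does not separate these cases, so a practical gap enters the change-from-baseline model as lost function.

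The SAP draws this distinction for the primary endpoint and for the timed tests, and its own remote-visit provisions foresee limits on testing. Nothing planned later would show how far the PUL result depends on the rule, because the sensitivity analyses, including those for COVID-19, cover only the primary and secondary endpoints. What is at stake is the accuracy of one additional endpoint.

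**Working it through.** **1. The stated maximum.** Inputs from SAP section 2.6.3.2: 7 items, maximum 2 points each. 7 × 2 = 14, which matches the stated range of 0 to 14.

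**2. The rules side by side.**

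| Test (SAP section) | Not done, physically unable | Not done, other reason |
|---|---|---|
| NSAA (2.6.1) | item scored 0 | total missing |
| Timed tests (2.6.2) | speed 0 | no zero assigned |
| PUL battery, Item A not 6 (2.6.3.2) | item scored 0 | item scored 0 |

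The PUL row alone gives the same value in both columns. No other part of either document limits the PUL rule by reason.

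**3. Effect on one boy.** Loss = (score he would have had − 0), at most 2 points per item.
- One item: 2/14 = 14.3% of the Total's range.
- Two items: 4/14 = 28.6%.
- All seven: from 14 to 0.
- If the rule were also applied to the sum of Items 1 and 2 (range 0 to 4), one item: 2/4 = 50%.

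**4. Effect on one arm's mean (illustration only).** Let *f* be the share of boys in the Total analysis with one such item, and *m* the mean score that item would have had. Shift in the mean Total at that visit = −*f* × *m*. The documents give neither value, so these are assumptions:
- *f* = 0.02, *m* = 1: −0.02 points
- *f* = 0.05, *m* = 2: −0.10 points
- *f* = 0.10, *m* = 2: −0.20 points
- *f* = 0.20, *m* = 2: −0.40 points

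**5. Effect on the difference between arms.** With *m* = 2 in both arms, the difference shifts by 2 × (share in one arm − share in the other), against the arm with more gaps.
- Gap of 5 percentage points: 2 × 0.05 = 0.10 points.
- Gap of 10 percentage points: 2 × 0.10 = 0.20 points.
- Equal shares: 0.

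These figures apply to boys in the Total analysis, not to the whole Full Analysis Population.

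**The case against.** The best defence is that this is a pre-specified convention for an additional endpoint. Different instruments may have different missing-item rules, so the SAP does not contradict itself. Most boys are expected to score 6 and skip the battery. Remote tests are run by trained evaluators, and nothing shows that any PUL item could not be done remotely. Affected visits can be partly traced, because efficacy data are listed by patient and the COVID-19 listing marks remote efficacy visits and has a comment field. All of this stands, and it limits the point. It does not make 0 a correct score for a task that was not attempted.

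A reader might infer more than the documents support:
- **Muscle strength as a third contrast.** SAP section 4.10.3 says: "If either the left or right value is missing the value will be the non-missing score". That rule does not use zero, but it does not ask the reason either, so it is no example of reason-specific handling.
- **An undefined score.** The words about an overall score most naturally mean the 0 to 14 Total defined in the same section. The 50% figure for Items 1 and 2 rests on a less natural reading.
- **False gains from gaps at baseline in remote visits.** Appendix 2 concerns Weeks 39 and 52 only, so remote testing cannot cause a baseline gap.
- **A Total of 0 when PUL was not done at all.** A literal reading allows this, but section 4.10.3 analyses PUL in a similar manner to section 4.10.1, which uses observed cases without imputation. One sentence would exclude that reading.

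**Conclusion.** The concern holds as a minor point. As written, the rule turns a PUL battery item not done for a non-physical reason into a recorded loss of up to 2 of 14 points for that boy. The NSAA and timed-test rules avoid this error.

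The effect on the Total is confined to boys who do not score 6 on Item A, presumably a small subset; the documents give no count. The size and direction of any between-arm bias are unknown, since no missing-item rate is given. The 0.10 to 0.20 point shifts rest on assumed gaps of 5 to 10 percentage points and on every missed item otherwise scoring 2. Equal missingness cancels on average.

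A reader might infer that the trial's efficacy conclusion is at risk. It is not: SAP section 4.2.5 tests only the NSAA and the three timed-test speeds, so no primary or secondary conclusion changes.

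**What to change.** In SAP section 2.6.3.2, before unblinding:
- Score a PUL battery item 0 only when it was not done because the boy was physically unable. Otherwise set the item and the Total to missing at that visit, as for the NSAA.
- State that a PUL not performed at all at a visit is missing and is handled as observed case.
- State that the same rule applies to the sum of Items 1 and 2. The existing handling of an Item A score of 6 stays.
- If the reason not done was not recorded for PUL, present both versions, missing and zero-scored. Scoring 0 can bias the result down when the gap was practical. Leaving it missing can bias the result up when the gap was due to inability. Neither alone is safe.

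The cost is one derivation rule, a few sentences and slightly more missing PUL data. The first option needs a recorded reason. The documents show such a field for the timed tests but not for PUL, so this should be checked first.
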